4 INVESTIGATIONAL PLAN

4.1 Overall Study Design and Plan

To effectively address the Primary and Secondary Objectives of this interventional study, we will enroll subjects, age 3 through 16 years, either sex, any race, any ethnicity with a serum IgE [UniCAPTM] to egg of $\geq 5 \text{ kU}_{\text{A}}/\text{L}$ [determined by UniCAPTM within the past 12 months]. All subjects will have documented consent and assent as is appropriate. Females of childbearing age will use appropriate birth control. These subjects will be recruited from 5 sites. All eligible subjects will receive the double-blind placebo controlled baked egg OFC. Approximately the first 40 individuals who do not pass this initial baked egg food challenge will be assigned to Egg OIT. Enrollment in this group will be capped at approximately 40 individuals though those consented but not yet challenged when this group reaches 40 will be allowed to proceed and if they fail the baked egg challenge will be assigned to the egg OIT assignment group. This may result in slightly over 40 cases in this group which is acceptable. Individuals who pass the baked egg OFC will then have an initial egg OFC. Those who have dose-limiting symptoms at a cumulative dose of \leq 1444 mg egg white protein will be randomized 1:1 to Baked Egg or Egg OIT. Those who successfully consume more than 1444 mg of egg white protein on the OFC will not be eligible for the study and will be followed per local standard of care.

Those assigned or randomized to Egg OIT will escalate the dose of egg white solid to achieve the desired maintenance dose of 2500 mg. Those randomized to the Baked Egg group will continue on the baked egg product for the remainder of the study.

A schematic is presented below:

- 12 -This is a Privileged and Confidential Communication Prepared by the EMMES Corporation

For the purposes of this study, clinical details and blood samples will be collected at specified intervals. If a subject is removed from therapy because of failing escalation or build-up, a blood sample for mechanistic studies will be obtained within approximately 1 week of removal from therapy.

The Baked Egg Group

The Baked Egg group will use approximately 2 gm of baked egg as a daily dose throughout the study as described below.

Baked egg therapy will consist of a muffin or equivalent (1/3 of egg in serving, approximately 2 gm).

Home baked products will have no more than 2 eggs per batch of recipe (yield 6 servings). Serving size is indicated by the yield of the recipe. Products will be baked for 25-50 minutes at 325-425 degrees Fahrenheit. Recipes will be provided. The daily dose can be administered at a single sitting or divided throughout the dosing day. Adjustments in the daily dosing may be made at the investigators discretion based on symptoms experienced by the subjects in the baked egg group.

Dietary information will be provided to the subject regarding allowed consumption of various commercial foods consistent with approximately 2 gm of baked egg per daily dose. Subjects in this arm will be encouraged to ingest "safe" commercial products in addition to their daily 2 gm intake of baked egg protein. These foods will be recorded on the daily logs.

The Egg OIT Groups

The egg OIT (eOIT) treatment is administered in 2 treatment groups, eOIT-Randomized and eOIT-Assigned, that may experience different paths for OIT treatment. The group randomized to receive eOIT treatment that have passed the baseline baked egg OFC (eOIT-Randomized) and the group assigned to receive eOIT (eOIT-Assigned) that have failed the baseline baked egg OFC. The group that fails the baked egg challenge may be more sensitive to egg dosing, and may experience more reactivity and adverse reactions. These subjects will stop at 12 mg egg white solid on the initial day escalation and thereby have a slightly slower escalation time course.

The egg OIT treatment is comprised of an initial escalation day, an initial build-up phase to last a maximum of 44 weeks, and followed by at least 8 weeks of daily therapy at the maximum achieved dose (350 mg - 2500 mg egg white solid).

Dosing Schedule for Egg OIT

Initial Day	Initial Day Escalation Schedule			
Dose no.	Egg white solid dose (mg)	Cumulative Egg dose (mg)*		
1	0.1 mg	0.1 mg		
2	0.2 mg	0.3 mg		
3	0.4 mg`	0.7 mg		
4	0.8 mg	1.5 mg		
5	1.5 mg	3.0 mg		
6	3.0 mg	6.0 mg		
7	6.0 mg	12 mg		
8	12 mg	24 mg		
9	25 mg	49 mg		

* If no de-escalation

Frequency standard every 30 min

Subjects at the end of the first day, tolerating less than 3 mg single dose, will be considered an initial day escalation desensitization failure.

The Egg OIT assignment group (that failed the Baked Egg challenge) will only escalate to 12 mg maximum on Day 1.

Subjects tolerating only 3, 6 or 12 mg single dose will go home on the greatest tolerated dose to be given daily (first dose given in Clinical Research Center under observation). All escalations will occur no sooner than 2 weeks and single dose increases in the Clinical Research Center from 3 to 6 to 12 to 25 mg will be attempted. These doses will be weighed doses in individual vials until the maximum 25 mg dose is reached.

All subjects will return on Day 2 and receive their maximum tolerated dose under direct observation.

Subjects with moderate symptoms observed on Day 2 will return on Day 3 for the next lower dose under observation in the Clinical Research Center or monitored clinic setting.

Doses on Day 2, 3, and 4 must be at least 3 mg or the subject will be considered an escalation failure.

Dose #	Dose egg white solid	Dose Method	Interval (weeks)	% Increase
8	12 mg	Vial	2	
9	25 mg	Vial	2	108%
10	50 mg	capsule*	2	100%
11	75 mg	capsule	2	50%
12	100 mg	capsule	2	33%
13	150 mg	capsule	2	50%
14	225 mg	capsule	2	50%
15	260 mg	scoop 0 [†]	2	15%
16	350 mg	scoop 1	2	35%
17	450 mg	scoop 2	2	30%
18	550 mg	scoop 3	2	20%
19	700 mg	scoop 4	2	25%
20	830 mg	scoop 5	2	20%
21	1100 mg	scoop 6	2	30%
22	1320 mg	scoop 7	2	20%
23	1720 mg	scoop 8	2	30%
24	2130 mg	scoop 9	2	25%
25	2500 mg	scoop 10	2	15%
* Capsul appropria	es are open te food.	ed and conte	nts sprinkled	over an age

Those subjects who achieved a dose of 2500 mg egg white solid during the initial build-up period will continue maintenance therapy for up to 12 months after the 1 year 7444 mg egg white protein OFC. Those subjects who achieved less than 2500 mg during the initial buildup phase will be escalated from their maintenance dose (pre-1-year 7444 mg egg white protein OFC) up to 2500 mg, if tolerated, following the

leveling.

same escalation time table from the initial build-up phase. No dose escalation will be performed within 1 month of a subject's planned 2 year 7444 mg egg white protein OFC.

Follow-up OFCs

At 1 year:

Those subjects still on active treatment (baked egg or egg OIT) will have a 7444 mg egg white protein OFC on therapy at 1 year to identify desensitized individuals.

At 2 years:

Those subjects still on active treatment (baked egg or egg OIT) will have a 7444 mg egg white protein OFC on therapy at 2 years. Those subjects still on active therapy, but escalating doses, will discontinue escalation for 1 month prior to their 2 year 7444 mg egg white protein OFC and will be maintained on their highest tolerated dose. Those who pass the 2 year egg 7444 mg egg white protein OFC on therapy will have a repeat 7444 mg egg white protein OFC after 8-10 weeks off therapy to test for sustained unresponsiveness. If they pass this OFC off therapy (including open feeding), they will add egg to their diet and will be followed at 3 months by phone and at 6 months in clinic to assess their egg diet history and reactivity status to egg.

If they fail the 2 year 7444 mg egg white protein OFC on or off therapy, they will stop therapy and the study physician will review treatment options.

4.2 Discussion of Study Design, Including the Choice of Control Groups

The design considers important safety issues:

- All dose escalations will be supervised in the clinic.
- The Egg OIT assignment group (that failed the baked egg challenge) will only escalate to 12 mg egg white solid maximum during the initial escalation on Day 1.
- OFC can delineate individuals who can ingest egg safely in a supervised setting.
- The relationship of egg-specific IgE to OFC results is unknown in individuals consuming baked egg or 350 2500 mg of egg white solid daily for up to a year. Thus, after long-term therapy, an egg OFC will be needed to determine sustained unresponsiveness irrespective of their egg-specific IgE level, and this will be performed safely in a supervised setting.

In addition, study enrollment will be suspended pending expedited review of all pertinent data by the NIAID DSMB if the following occurs:

- Any death related to Baked Egg or Egg OIT dosing.
- More than 1 severe anaphylactic reaction (see Appendix 3 of the protocol) related to Baked Egg or Egg OIT dosing at any stage of the protocol.
- More than 3 treatment-related non-anaphylaxis severe adverse events (including EoE).
- More than 1 serious suspected adverse reaction occurs (serious and related).
- More than 3 subjects who require more than 1 injection of epinephrine for a single study product related allergic reaction during the study therapy.

4.3 Selection of Study Population

The study population was selected based on prior studies of egg OIT. A pre-enrollment study OFC was required to demonstrate evidence of egg allergy.

Detailed study inclusion and exclusion criteria are listed below.

4.3.1 Inclusion Criteria

Subjects who meet *all* of the following criteria are eligible for enrollment as study subjects:

- Age 3 through 16 years with a serum IgE [UniCAPTM] to egg of \geq 5 kU_A/L [determined by UniCAPTM within the past 12 months].
- Reacting to the baked egg challenge OFC with dose limiting symptoms (approximately 40 subjects), OR
- Reacting on an initial egg OFC with dose limiting symptoms to a cumulative dose of 1444 mg egg white protein or less after passing the initial baked egg OFC.
- Written informed consent from subject and/or parent/guardian.
- Written assent from all subjects as is appropriate.
- All females of child-bearing age must be using appropriate birth control.

4.3.2 Exclusion Criteria

Subjects who meet *any* of these criteria are *not* eligible for enrollment as study subjects:

- History of anaphylaxis to egg resulting in hypotension, neurological compromise or mechanical ventilation.
- Chronic disease (other than asthma, atopic dermatitis, rhinitis) requiring therapy (e.g., heart disease, diabetes).
- Active eosinophilic gastrointestinal disease in the past 2 years.
- Participation in any interventional study for the treatment of food allergy in the past 6 months.
- Subject is on "build-up phase" of immunotherapy (i.e., has not reached maintenance dosing). Subjects tolerating maintenance allergen immunotherapy can be enrolled.
- Severe asthma (2007 NHLBI Criteria Steps 5 or 6, see Appendix 2 of the protocol).
- Mild or moderate (2007 NHLBI Criteria Steps 1-4) asthma with any of the following criteria met:
 - FEV1 <80% of predicted, or FEV1/FVC <75%, with or without controller medications (only for age 6 or greater and able to do spirometry), or
 - $\circ~$ ICS dosing of >500 mcg daily fluticasone (or equivalent inhaled corticosteroids based on NHLBI dosing chart), or
 - \circ 1 hospitalization in the past year for asthma, or
 - \circ 1 ER visit in the past 6 months for asthma.
- Use of steroid medications (IV, IM or oral) for asthma in the following manners:
 - \circ history of daily oral steroid dosing for >1 month during the past year, or
 - burst or steroid course in the past 3 months, or
 - >2 burst oral steroid course in the past year.
- A burst of IV, IM or oral steroids of more than 2 days for an indication other than asthma in the past 30 days.
- Inability to discontinue antihistamines for the initial day of escalation, skin testing or OFC.

- Use of omalizumab or other non-traditional forms of allergen immunotherapy (e.g., oral or sublingual) or immunomodulator therapy (not including corticosteroids) or biologic therapy (e.g., infliximab, rituximab, etc.) within the past year.
- Use of β-blockers (oral), angiotensin-converting enzyme (ACE) inhibitors, angiotensin-receptor blockers (ARB) or calcium channel blockers.
- Use of investigational drug within 90 days or plan to use investigational drug during the study period.
- Pregnancy or lactation.

4.4 Treatments

4.4.1 Treatments Administered

Two treatments will be administered daily for this study, egg oral immunotherapy (eOIT) for participants in the eOIT-Randomized and eOIT-Assigned groups, and baked egg for participants in the Baked Egg group.

Baked egg therapy will be prepared using commercially available food ingredients and prepared according to pre-specified recipes, cooking temperatures, and times to administer consistent doses of baked egg.

Baked egg therapy will consist of a muffin or equivalent (1/3 of egg in serving or approximately 2 gm of protein). Home baked products will have no more than 2 eggs per batch of recipe (yield 6 servings). Serving size is indicated by the yield of the recipe. Products will be baked for 25-50 minutes at 325-425 degrees Fahrenheit. Recipes will be provided. The daily dose can be administered at 1 sitting or divided throughout the dosing day. These methods are outlined in the manual of procedures and instructions for the subjects and their families.

Study drug (commercially available egg white solid) will be centrally packaged, stored and distributed by EMINENT Services Corporation. Central manufacturing will consist of weighing individual doses of the egg white solid into vials or capsules and providing bulk egg white solid for use with scoops. A 37% egg white solid blended product as described in the manufacturing section of the IND will be used to provide specified dose levels in capsules whereas 100% egg white solid will be used to provide specified dose in vials or in bulk product.

Initial day dose escalation will be packaged in individual vials with each dose weighed. Initial day escalation kits will have 2 doses of each vial up to 25 mg egg white solid. Individual dose level kits will have 21 vials per kit. Kits will be used until a dose of 50 mg egg white solid is achieved. Starting at doses of 50 mg, the egg white solid doses will be packaged in pull-apart capsules with the appropriate dose in each capsule. One capsule will be used for each day's dose. Capsules will be packaged in bottles of 21.

Starting at doses of 350 mg egg white solid, bulk powder will be dispensed with a dose-specific scoop. Subjects will be instructed to use 1 scoop per day that is leveled across the top of the scoop. The bulk product will be in a supply of 500 gm. All study product will be packaged at the central manufacturer. Study drug will be shipped by the central manufacturer to the site pharmacist for distribution to the site study personnel. The site pharmacist will dispense study drug in a manner consistent with the current dose level and treatment assignment.

All study drug will be labeled at the central manufacturer and shipped to the local pharmacy for distribution to the study subjects. The product will be labeled with the numbered dose level and package number.

Every attempt to use a single lot of commercially available egg white solid will be made. If a new lot is required, and any subject is in an escalation phase of the study, they will have a single observed in clinic dose reduction with the new lot. Escalation to their previous dose may occur in 1 week if the subject has the same or fewer symptoms than those occurring with the previous lot.

4.4.2 Method of Assigning Participants to Treatment Groups (Randomization)

Randomization was performed using an online data system with participants allocated in a 1:1 fashion to eOIT or baked egg consumption stratified by site. The first 40 participants to fail the initial baked egg challenge were assigned to receive eOIT. Further baked egg OFC failures were considered screen failures and not enrolled.

4.4.3 Blinding

This study is unblinded.

5 SAMPLE SIZE CONSIDERATIONS

The sample size target for the randomized portion of the study is 96 individuals with 1:1 random assignment to Baked Egg and Egg OIT. The sample size was selected to determine whether a difference exists between the treatment groups in the primary endpoint rate for the sustained unresponsiveness-focused portion of the study. Specifically, the sample was designed to have 85% power to detect with a two-sided 5% level test, a difference between a 40% and 70% sustained unresponsiveness rate. While a small dropout rate may occur, we will use all randomized cases who initiate treatment in the intent-to-treat analysis of the primary endpoint; failures associated with noncompliance are include in the denominator for event rates above. This sample size is sufficient to address the secondary endpoint of the desensitization components of the study for event rate differences of comparable size.

The subset of individuals who are not baked egg tolerant at baseline comprise a selected group of individuals where Egg OIT will be examined. The size of the group will be capped at approximately 40 subjects. The study cohort should be useful for both clinical and mechanistic study with approximately 40 such individuals enrolled. The 2 year sustained unresponsiveness rate will be compared to historical experience as well as the protocol's randomized Egg OIT arm. Mechanistic studies will be examined to determine if baseline immune system responses are similar in both Egg OIT groups. Immune parameter

changes will be examined to determine if tolerant and non-tolerant cases have response profiles that are parallel for the 2 strata.

6 GENERAL STATISTICAL CONSIDERATIONS

6.1 General Principles

All continuous variables will be summarized using the following descriptive statistics: n (non-missing sample size), mean, standard deviation (or median and interquartile range (IQR) as appropriate), maximum and minimum. Transformations of immune results may be required and appropriate transformations will be applied (e.g., log 10 transform). The frequency and percentages (based on the non-missing sample size) of observed levels will be reported for all categorical measures. Where appropriate, summary tables will be structured with a column for each treatment and assignment group in order (Baked Egg, eOIT – Randomized and eOIT - Assigned) and will be annotated with the total population size relevant to that table/treatment, including any missing observations.

6.2 Timing of Analyses

The primary analysis will take place when all participants have completed the appropriate Year 2 OFCs and the OFCs have been appropriately monitored. The final analysis will take place when the last long term follow-up questionnaire is completed (targeted September 2018).

6.3 Analysis Populations

The efficacy analysis population will consist of randomized participants who initiate treatment as well as all participants enrolled in the eOIT – Assigned group who initiate treatment. The safety population may vary based on time period and will consist only of treated participants. Mechanistic analyses will consider those with available samples.

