Endpoints and analysis: The primary endpoint of the study will be the development of sustained unresponsiveness to a 7444 mg egg white protein OFC followed by open consumption of a whole egg, 8-10 weeks after discontinuing 2 years of daily Baked Egg or Egg OIT. OFCs will be conducted in a supervised setting and safety parameters will be carefully monitored.

Individuals off therapy for 8-10 weeks, successfully demonstrating consumption of 7444 mg egg white protein OFC without dose-limiting symptoms followed by consuming a whole egg will be considered "successes." All others will be considered "failures" with respect to this endpoint. Among all subjects randomized, the number of subjects on each treatment successfully demonstrating sustained unresponsiveness will be compared to those failing to tolerate this quantity by Chi-square analysis.

Expected outcome/potential limitations: The expected outcome is that 40% of Baked Egg vs. 70% of Egg OIT subjects will tolerate 7444 mg egg white protein OFC, 8-10 weeks after discontinuing Egg OIT or Baked Egg products. The primary limitation to the study is the possibility that we have over-estimated the number of subjects who will tolerate the therapies or subjects do not adhere to dietary restrictions.

Secondary Objectives:

1. Determine the percentage of subjects who can successfully consume without dose limiting symptoms at least 4444 mg egg white protein of a 7444 mg egg white protein OFC after the initial desensitization phase of approximately 1 year of the study and at 2 years.

Rationale: Subjects allergic to egg often have accidental allergic reactions to small amounts of egg in other foods. Generally, the amount of egg causing these accidental allergic reactions is less than 500 mg of egg protein. Previous studies suggest that the continuous administration of a food allergen leads to a "desensitized" state in which an allergic subject will be unresponsive to the ingestion of a food allergen as long as they continue to ingest a small amount of the food on a daily basis.⁸⁰ Food challenges of egg white solid can be done to determine if accidental ingestions of typical amounts of egg could occur without adverse effects.

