4.3 Premature Subject Termination from the Study

4.3.1 Criteria

No subject initiating therapy in this trial will be replaced.

Any subject may be prematurely terminated from additional allergen exposures, but maintained on longitudinal follow-up for the following reasons:

• Anaphylaxis resulting in hypotension, neurological compromise or mechanical ventilation secondary to Baked Egg or Egg OIT dosing or any egg food challenge.

Any subject deemed to have severe symptoms and receives aggressive therapy at any time should be discontinued from further therapy, including the following:

- Poor control or persistent activation of secondary atopic disease (e.g., AD, asthma).
- Started on ARBs, ACE inhibitors, beta-blockers, or other prohibited meds and there are no alternative meds available per the prescribing doctor, they will be removed from further treatment.
- Pregnancy.
- Egg OIT Group subjects:
 - Circumstances (e.g., concurrent illness, such as gastroenteritis) requiring missed Egg OIT maintenance dosing of >7 consecutive days (this does not include subjects intentionally removed from therapy to administer an OFC off therapy).
 - Non-adherence with home Egg OIT dosing protocol (excessive missed days; i.e., >3 consecutive days missed on 3 occasions), would be a safety issue warranting discontinuation.

Any subject may be prematurely terminated from the study if:

- The subject elects to withdraw consent from all future study activities, including followup.
- The subject is "lost to follow-up" (i.e., no further follow-up is possible because attempts to reestablish contact with the subject have failed).
- The subject has biopsy documented Eosinophilic Esophagitis (EoE).

• The subject dies.

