9.1 Study Endpoint Assessment

9.1.1 Primary Endpoint

The primary endpoint is defined in Section 3.1.1. For the randomized portion of the study an intent-to-treat analysis will be performed. Sustained unresponsiveness can only be demonstrated after discontinuation of active therapy for 8-10 weeks. Individuals successfully demonstrating dose limiting symptom-free consumption of 7444 mg egg white protein by OFC (i.e., dose-limiting symptom-free dosing followed by meal size portion) will be considered successes. All others will be considered to be failures with respect to this endpoint. Analysis will be via the Chi-square test.

9.1.2 Secondary Endpoints

The secondary endpoints are defined in Section 3.1.2.

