9.3 Sample Size and Power Calculations

The sample size target for the randomized portion of the study is 96 individuals with 1:1 random assignment to Baked Egg and Egg OIT. The sample size was selected to determine whether a

difference exists between the treatment groups in the primary endpoint rate for the sustained unresponsiveness-focused portion of the study. Specifically, the sample was designed to have 85% power to detect with a two-sided 5% level test, a difference between a 40% and 70% sustained unresponsiveness rate. While a small dropout rate may occur, we will use all randomized cases who initiate treatment in the intent-to-treat analysis of the primary endpoint; failures associated with noncompliance are include in the denominator for event rates above.

This sample size is sufficient to address the secondary endpoint of the desensitization components of the study for event rate differences of comparable size.

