1 PREFACE

The Statistical Analysis Plan (SAP) for *Oral Desensitization to Egg with Subsequent Induction of Sustained Unresponsiveness for Egg-Allergic Children using Baked Egg or Egg Oral Immunotherapy (OIT)* describes and expands upon the statistical information presented in the protocol. This trial is sponsored by the NIAID and was designed and implemented at NIAID funded CoFAR sites. The Emmes Corporation serves as the SACCC for CoFAR.

This document describes all planned analyses and provides reasons and justifications for these analyses. A listing of tables, listings, and figures planned for the final analyses are provided in a separate document. Regarding the final analyses and Clinical Study Report (CSR), this SAP follows the International Conference on Harmonisation of Technical Requirements for Registration of Pharmaceuticals for Human Use (ICH) Guidelines, as indicated in Topic E3 (Structure and Content of Clinical Study Reports), and more generally is consistent with Topic E8 (General Considerations for Clinical Trials) and Topic E9 (Statistical Principles for Clinical Trials). The structure and content of the SAP provides sufficient detail to meet the requirements identified by the FDA and ICH, while all work planned and reported for this SAP will follow internationally accepted guidelines published by the American Statistical Association and the Royal Statistical Society for statistical practice.

This document contains three sections: (1) a review of the study design, (2) general statistical considerations, and (3) comprehensive statistical analysis methods for efficacy and safety outcomes. Any deviation from this SAP will be described and justified in protocol amendments and/or in the CSR, as appropriate. The reader of this SAP is encouraged to also review the study protocol for details on conduct of the study and the operational aspects of clinical assessments.

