3.3 Study Definitions and Derived Variables

The primary endpoint of the study will be the development of sustained unresponsiveness to a 7444 mg egg white protein OFC followed by open consumption of a whole egg, 8-10 weeks after discontinuing 2 years of daily Baked Egg or Egg OIT. OFCs will be conducted in a supervised setting and safety parameters will be carefully monitored. Individuals off therapy for 8-10 weeks, successfully demonstrating consumption of 7444 mg egg white protein during OFC without dose-limiting symptoms followed by an open feeding of a meal-sized portion of egg are considered successes; those not receiving the open feeding of a meal-sized portion of egg due to site error are also considered successes. Individuals who do not attempt this off therapy OFC or do not successfully consume 7444 mg egg white protein for this off therapy OFC will be considered "failures" with respect to this endpoint.

For the desensitization endpoint, all individuals with an SCD \geq 4444 mg egg white protein will be considered successes All others will be considered "failures" with respect to this endpoint.

For safety endpoints, the pre-defined secondary endpoint is the incidence of serious adverse events. Additional safety endpoints of interest include the incidence of adverse events related to dosing which will be estimated from the dosing symptom logs. For the first 12 months on therapy, or for the time until reaching the maximum maintenance dose if this occurs after 12 months, all dosing symptom logs are required to be submitted. Otherwise, only doses with reactions or missed doses have dosing symptom logs reported in the data system. All non-reported doses are assumed to have been successfully administered without reaction or treatment required. To estimate the number of doses administered, the following algorithm will be used:

Through Week 52: Date of last dose is calculated as the minimum of the completion date of the Week 52 OFC, the drug discontinuation date and the study withdrawal date minus one day. It is assumed that a dose would not occur on the day of Week 52 OFC.

The number of expected doses will be calculated as days from treatment initiation to date of last dose and the percent of doses administered will be calculated as administered doses/expected doses.

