7 STUDY PARTICIPANTS

7.1 Participant Disposition

Participant disposition will be described in tables by site and treatment group.

A CONSORT diagram will describe the participant disposition and loss to follow-up through the course of the study.

7.2 **Protocol Deviations**

Participant-specific protocol deviations will be described by individual, treatment group and site. Site specific deviations will be described by site. Listings will include a description of the deviation and any action taken as a result.

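### Protocol 2.1 compares all randomised subjects, but Protocol 9.3 and SAP 5 and 6.3 analyse only those who start treatment, and no all-randomised analysis is planned

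*SAP*

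**What the plan says.** Current text in the two documents gives two denominators for the primary comparison.

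- **All randomised.** Protocol 2.1, under the primary objective, reads "Among all subjects randomized, the number of subjects on each treatment successfully demonstrating sustained unresponsiveness will be compared to those failing", and counts everyone who is not a demonstrated success as a failure.
- **Starters only.** Protocol 9.3 says "we will use all randomized cases who initiate treatment in the intent-to-treat analysis of the primary endpoint", and SAP 5 repeats this. SAP 6.3 makes it the efficacy population: "The efficacy analysis population will consist of randomized participants who initiate treatment", together with starters in the non-randomised assigned group.
- **Neutral.** Protocol 9.1.1 says "For the randomized portion of the study an intent-to-treat analysis will be performed" and treats all non-successes as failures. This fits either reading.

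SAP 8.3.1 specifies the chi-square (or Barnard) test without restating the population. Its only secondary analysis of the primary endpoint compares the two Egg OIT groups. SAP 3.3 counts as failures "Individuals who do not attempt this off therapy OFC or do not successfully consume 7444 mg egg white protein" at the off-therapy challenge, but this cannot bring back a non-starter whom SAP 6.3 has already removed.

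Neither document defines the start of treatment. On replacement, Protocol 4.3.1 says "No subject initiating therapy in this trial will be replaced" and is silent on randomised subjects who never start.

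**The concern.** A randomised subject who never takes a dose is a failure under Protocol 2.1 and is absent under SAP 6.3. The reported primary result may therefore not be the one that Protocol 2.1 describes.

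The exclusion happens after randomisation in an unblinded trial (Protocol 6.10, SAP 4.4.3). Families know their arm before they start, and the first step differs. Egg OIT begins with a supervised multi-dose escalation day (Protocol 6.4). Baked Egg families attend on Day 1 to show their products and then dose at home (Protocol Appendix 1.B). If families decline one of these more often, removing them disturbs the randomised comparison. Missing outcomes do not force the exclusion, because the failure rule in SAP 3.3 could score a non-starter directly.

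**Working it through.** **Inputs from the documents.** 96 randomised 1:1, so 48 per arm; success rates 40% and 70%; two-sided 5% test; planned power 85% (Protocol 9.3, SAP 5). Sustained unresponsiveness in the predecessor egg OIT trial was 11/40 = 27.5% (Protocol 1.1).

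**Assumptions.** The number of non-starters k is not given, so it is varied. All k fall in one arm unless stated. A 55% rate, the midpoint of 40% and 70%, is added as a third null rate.

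**1. The plan's own figure.** Pooled-variance formula: power = Φ{[d − 1.96·√(2p̄(1−p̄)/n)] / √[(p₁(1−p₁)+p₂(1−p₂))/n]}. With d = 0.30, p̄ = 0.55, n = 48, this is (0.30 − 1.96 × 0.1016)/0.0968 = 1.04, so power is 0.851. Exact enumeration of the uncorrected chi-square test gives 0.854. The stated 85% reproduces, and the sample size is not in question.

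**2. Type I error on the starter set, with equal all-randomised rates r.** If non-starters are failures, the starters in the affected arm have rate r × 48/(48 − k). For r = 0.40 and k = 2 that is 0.40 × 48/46 = 0.417, a lift of 1.7 points. Summing the probabilities of all tables from Bin(48, r) and Bin(48 − k, r × 48/(48 − k)) with chi-square above 3.8415 gives:

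| k in one arm | r = 27.5% | r = 40% | r = 55% |
|---|---|---|---|
| 0 | 5.16% | 4.95% | 5.10% |
| 1 | 5.09% | 5.47% | 5.35% |
| 2 | 5.34% | 5.25% | 5.42% |
| 3 | 5.65% | 5.39% | 6.61% |
| 5 | 6.30% | 6.87% | 9.29% |
| 7 | 7.32% | 9.56% | 14.73% |

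At k = 1 to 3 the affected arm's rate rises by 0.6 to 3.7 points. The k = 7 row is an extreme: 7/48 = 14.6%, close to the predecessor trial's whole egg OIT withdrawal before 24 months (6/40 = 15%, Protocol 1.1). Losing 1 to 3 from both arms gives 4.6% to 5.3%, so part of the movement at small k is discreteness.

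**3. The same check with equal rates among starters.** At k = 1 to 3 the starter set gives 4.8% to 5.4%, and the all-randomised analysis 4.9% to 6.1%.

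**4. Power on the starter set if 40% and 70% are all-randomised rates.** The affected arm's rate is rescaled by 48/(48 − k).

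| k | in Baked Egg: difference, power | in Egg OIT: difference, power |
|---|---|---|
| 1 | 29.1 points, 0.82 | 31.5 points, 0.89 |
| 2 | 28.3 points, 0.80 | 33.0 points, 0.91 |
| 3 | 27.3 points, 0.75 | 34.7 points, 0.94 |

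**5. How a result could turn (invented data).** Take Baked Egg 19/48 and 28 Egg OIT successes, with 2 of the 48 Egg OIT subjects never starting. Starters only, 19/48 v 28/46: chi-square 4.26, p = 0.039. All randomised, 19/48 v 28/48: chi-square 3.38, p = 0.066.

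**The case against.** The SAP follows the protocol's own statistical section. Protocol 9.3 states the restriction, SAP 5 repeats it, and the contrary text is one sentence in the objectives. The rule is pre-specified and turns on starting treatment, not on outcome. The window is short, from randomisation to first dose, and families have by then completed two food challenges, so non-starters may be rare. Day 1 escalation failures and later dropouts stay in as failures. All of this stands. It limits the size of the problem, but it does not remove the conflict with Protocol 2.1 or supply the missing analysis.

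The calculations do not favour one population either. Every departure from about 5% assumes one-sided non-starting. At k = 1 to 3, eight of the nine cells lie between 5.1% and 5.7%. If the rates are equal among starters, the starter set holds its level and the all-randomised analysis drifts slightly. The choice is one of estimand, and the case for all randomised is that Protocol 2.1 names it.

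Three stronger readings are tempting but not supported:

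- That Protocol 2.1 and SAP 6.3 put different sets under one intent-to-treat label. Neither uses the term. It appears in Protocol 9.1.1, Protocol 9.3 and SAP 5, and the last two state the restriction in the same sentence.
- That the undefined start of treatment leaves the denominator open to choice. This is mostly missing detail: SAP 3.3 requires all dosing logs for the first 12 months, so a first dose can be identified in both arms.
- That the SAP can simply depart from Protocol 9.3. SAP 1 says "Any deviation from this SAP will be described and justified in protocol amendments and/or in the CSR, as appropriate". This covers departures from the SAP, not departures of the SAP from the protocol.

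**Conclusion.** The conflict is in current text and is certain. Protocol 2.1 and the starter-only sections define different primary populations, and the SAP plans nothing on the Protocol 2.1 population. It should be fixed, though it is at the lower end of what warrants a change.

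A reader might infer that the primary result is biased or its error rate inflated. The documents do not show that. They give no non-starter count and no sign that starting differs by arm; the unblinded design and the different first steps only make it possible. With no non-starters the two analyses are identical. With 1 to 3, all in one arm, type I error is 5.1% to 6.6% under equal all-randomised rates, and power is 0.75 to 0.94 against 0.85 if 40% and 70% are all-randomised rates. These figures rest on the assumed k, on all non-starters falling in one arm, and on the uncorrected chi-square test.

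**What to change.** **Preferred.** Reconcile Protocol 2.1 and 9.3, and amend SAP 5 and 6.3 together with 9.3. Changing the SAP alone would only move the contradiction to Protocol 9.3. The randomised comparison should use all randomised participants in their assigned arm, with non-starters scored as failures under SAP 3.3. The starter set stays as a sensitivity analysis labelled modified ITT.

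**Fallback.** If Protocol 9.3 is not amended, or non-starting by arm is already known, keep starters as the primary set, label it modified ITT, and add the all-randomised comparison as a pre-specified sensitivity analysis. The second condition is a real possibility: SAP 4.4.2 describes randomisation in the past tense, and replacing the primary population once non-starting by arm is known would be open to criticism.

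**In either case.** State that initiation means the first recorded dose in each arm. Report non-starters by arm, and whether any were replaced, in the diagram already planned in SAP 7.1: "A CONSORT diagram will describe the participant disposition and loss to follow-up through the course of the study".

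**Cost.** No new data. The preferred route needs a protocol amendment and wording in two SAP sections. There is also a possible loss of power. If 40% and 70% were meant as rates among starters, Egg OIT successes follow Bin(48 − k, 0.70) over a denominator of 48. One, two or three Egg OIT non-starters then give differences of 28.5, 27.1 and 25.6 points and exact power of 0.82, 0.78 and 0.73, against 0.85, 0.84 and 0.85 on the starter set.
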